6.7.1. Historical Illness and Pre-existing Conditions

Historical illnesses are defined as those conditions recorded in the Preexisting Conditions and Medical History electronic case report form (eCRF) with an end date prior to the informed consent date. The number and percentage of patients with selected historical diagnoses will be summarized for the OLLI population, also they will be summarized by treatment group using the DBW population. Historical diagnoses will be categorized using the Medical Dictionary for

Regulatory Activities (MedDRA[®], most current available version) algorithmic Standardized MedDRA Queries (SMQs) or similar predefined lists of Preferred Terms (PTs) of interest.

Preexisting conditions are defined as those conditions recorded in the Preexisting Conditions and Medical History eCRF or the Adverse Events eCRF with a start date prior to the date of informed consent and an end date after informed consent or missing. For events occurring on the day of the first dose of study treatment, the date and time of the onset of the event will both be used to determine if the event was preexisting. Conditions with a partial or missing start date (or time if needed) will be assumed to be ‘not preexisting’ unless there is evidence, through comparison of partial dates, to suggest otherwise. Preexisting conditions will be categorized using the MedDRA SMQs or similar predefined lists of PTs of interest. Frequency counts and percentages of patients with selected preexisting conditions will be summarized for the OLLI population, and also will be summarized by treatment group using the DBW population.

6.8. Treatment Compliance

Treatment compliance with investigational product will be summarized by treatment periods with corresponding population. Patients will be considered compliant for each treatment period if they miss <20% of the expected doses. Proportions of patients compliant will be summarized.

Similarly, patients will be considered noncompliant if they are judged by the investigator to have intentionally or repeatedly taken more than the prescribed amount of study medication.

Compliance in the period of interest up to Visit x will be calculated as follows:

$$\text{Compliance} = \frac{\text{total number of tablets (or weight of suspension) dispensed} - \text{total number of tablets (or weight of suspension) returned}}{\text{expected number of total tablets (or weight of suspension)}}$$

where

- Total number of tablets (or weight of suspension) dispensed: sum of tablets (or weight of suspension) dispensed in the period of interest prior to Visit x ;
- Total number of tablets (or weight of suspension) returned: sum of the tablets (or weight of suspension) returned in the period of interest prior to and including Visit x ;
- Expected number of tablets (or weight of suspension): number of days in the period of interest * number of tablets (or weight of suspension) taken per day = [(date of visit – date of first dose + 1) – number of days of temporary drug interruption] * number of tablets (or weight of suspension) taken per day

Descriptive statistics for percent compliance and noncompliance rates will be summarized for the OLLI population for Week 0 through Week 12 and will also be summarized for the DBW population by treatment group for Week 12 through Week 44. Subintervals of interest, such as compliance between visits, may also be presented. The number of expected tablets or suspension dispensed, tablets or suspension returned, and percent compliance may be listed by patient for Week 0 through Week 44.

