5.1.5. Post-Treatment Follow-Up Period

Patients who complete the study or discontinue early from the study will return for the post-treatment safety follow-up visit (Visit 801) approximately 28 days after the last dose of investigational product. Patients who enroll in the OLE study (JAHX) do not need to return for a follow-up visit.

Patients who have received at least 1 dose of investigational product, do not have a PedACR30 response rate at Week 12, experience a flare leading to discontinuation during the DBW (and are not moving to the OLE), or terminate participation early must have an early termination visit (ETV).

Patients who have discontinued investigational product but remain in the study for more than 28 days without investigational product will have an ETV if they chose to withdraw from the study; however, a separate follow-up visit (Visit 801) is not required.

Patients should not initiate new treatment during the post-treatment follow-up period. However, if patients or investigators must initiate a new treatment, patients should complete a Visit 801 prior to the first dose of the new therapy (if possible).

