7.6. Treatment Compliance

Patient compliance with study medication will be assessed at each visit (except Visit 3) during the treatment period (baseline through Week 44).

Patients treated with baricitinib or placebo will be considered noncompliant if they miss $\geq 20\%$ of the prescribed doses during the study (unless the patient's investigational product was withheld by the investigator for safety reasons).

Similarly, patients will be considered noncompliant if they are judged by the investigator to have intentionally or repeatedly taken more than the prescribed amount of study medication. Patients found to be noncompliant with the investigational product should be assessed to determine the reason for noncompliance and educated and/or managed as deemed appropriate by the investigator to improve compliance.

Patients will be counseled by study staff on the importance of taking the investigational product as prescribed, as appropriate.

Patient compliance will be further defined in the statistical analysis plan (SAP).

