6.1.3. Definition of OLLI and DBW Analysis Periods

The OLLI period starts at:

- The completion of Safety/PK assessment period for Safety/PK population patients
- The time of first age-based dose of baricitinib for OLLI population patients

The OLLI period ends for the following study events:

- Week 12 (Visit 9) for patients who do not meet the randomization criteria, or
- Visit of early discontinuation of study treatment in the OLLI period.

The DBW period starts at the time of randomization and ends at the following study events:

- Patient experience disease flare (defined in [Table JAHV.6.4](#))
- Week 44 (Visit 17) for patients who do not flare, or
- Visit of early discontinuation of study treatment in the randomized double-blind withdrawal period.

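### SAP 6.8 scores off-drug days between permanent discontinuation and the discontinuation visit as missed doses, so an adherent patient who stops early can be classed as noncompliant

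*SAP*

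**What the plan says.** SAP 6.8 defines compliance as the amount dispensed less the amount returned, divided by the amount expected. The expected amount is the "number of days in the period of interest" times the daily amount, and the day count is spelled out as "date of visit – date of first dose + 1) – number of days of temporary drug interruption". The classification rule is: "Patients will be considered compliant for each treatment period if they miss <20% of the expected doses". Results are summarised for the open-label lead-in (OLLI) period, and by treatment group for the DBW period.

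SAP 6.1.3 closes each period for a patient who stops drug. The OLLI period ends at the "Visit of early discontinuation of study treatment in the OLLI period", and the DBW period at the "Visit of early discontinuation of study treatment in the randomized double-blind withdrawal period".

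Protocol 7.6 sets the same 20% limit, but against prescribed doses, and makes an exception where "investigational product was withheld by the investigator for safety reasons". Protocol 5.1.5 foresees "Patients who have discontinued investigational product but remain in the study for more than 28 days without investigational product".

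For exposure, SAP Table JAHV.6.10 ends the DBW count at the last dose, not at a visit.

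**The concern.** The only days that the formula removes are those of temporary interruption. After permanent discontinuation no doses are prescribed, yet the day count runs on to the visit and each of those days enters the denominator as a dose that should have been taken. The numerator cannot grow, so compliance falls although the patient did nothing other than stop.

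Two other rules point the other way. Protocol 7.6 counts missed doses among those prescribed and excuses product withheld for safety; SAP 6.8 carries that over only as temporary interruption. The SAP's exposure rule treats the same patient as off drug from the last dose. A patient can therefore be off drug in the exposure table and overdue for drug in the compliance table over the same days.

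At stake is a descriptive figure, the proportion compliant by period and, in the DBW period, by arm. Some stops for adverse events would be shown there as poor adherence.

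**Working it through.** The documents give no compliance figure to reproduce, so the check applies the SAP 6.8 formula directly.

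**Assumptions.** The patient takes every dose up to the last dose on day *s* of the period. There is no temporary interruption. The first dose of the period is day 1. DBW visits fall every 28 days (Protocol Table JAHV.2), so with the formula's +1 they lie on days 29, 57, …, 225.

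**Formula.** With *g* days counted after the last dose up to and including the visit day, compliance = *s*/(*s* + *g*). The patient is noncompliant when *g*/(*s* + *g*) ≥ 0.20, that is, when *g* ≥ *s*/4. If the visit is on day *v*, this is the same as *s* ≤ 0.8*v*.

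**Count to the next scheduled DBW visit.**

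| Visit day *v* | Stop days before it | 0.8*v* | Noncompliant stop days | Number |
|---|---|---|---|---|
| 29 | 1–28 | 23.2 | 1–23 | 23 |
| 57 | 29–56 | 45.6 | 29–45 | 17 |
| 85 | 57–84 | 68.0 | 57–68 | 12 |
| 113 | 85–112 | 90.4 | 85–90 | 6 |
| 141 and later | 113–224 | below the first stop day of each interval | none | 0 |

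The total is 23 + 17 + 12 + 6 = 58 of 224 stop days (58/224 = 26%), none after day 90. Single cases:

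- stop on day 14, visit on day 29: 14/29 = 48.3%, noncompliant
- stop on day 42, visit on day 57: 42/57 = 73.7%, noncompliant
- stop on day 70, visit on day 85: 70/85 = 82.4%, compliant
- stop on day 154, visit on day 169: 154/169 = 91.1%, compliant

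**Fixed gap to the discontinuation visit.** A 7-day gap gives noncompliance when *s* ≤ 4 × 7 = 28, so 28/224 = 12.5% of stop days. The fewest on-drug days that keep the patient compliant are 29 for a 7-day gap, 57 for 14 days, 113 for 28 days and 141 for 35 days.

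**OLLI period** (visits at Weeks 2, 4, 8 and 12, same day convention). Visits are closer together at first, but there are fewer on-drug days to offset the gap:

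- 7/15 = 46.7%, noncompliant
- 21/29 = 72.4%, noncompliant
- 42/57 = 73.7%, noncompliant
- 70/85 = 82.4%, compliant

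**With the count ended at the last dose.** Compliance = *s*/*s* = 100% for every stop day, as it should be for a patient who missed nothing.

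**The case against.** The strongest reply is that the over-count is bounded. The formula is limited to the period of interest, and SAP 6.1.3 closes that period at the visit of early discontinuation. This stands, and it rules out several stronger readings.

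- *Expected doses run on to Week 44.* A reader might infer this from Protocol 5.1.5, or from the SAP 6.8 label giving the DBW summary as Week 12 through Week 44. Every stop by day 180 would then be noncompliant (0.8 × 225 = 180; 180/224 = 80%), and 28 days on drug would score 28/225 = 12.4%. SAP 6.1.3 does not support it: the label is the nominal span, and Protocol 5.1.5 sets follow-up visits without extending the treatment period. What remains open is which visit counts as the discontinuation visit for a patient who stays in the study off drug.
- *Patients who stop for an adverse event are noncompliant as a class.* They are not. It takes a gap of at least a quarter of the on-drug days.
- *About 13 of the 128 randomized patients are misclassified.* This takes the planning limit of 10% dropout (0.10 × 128 = 12.8) and assumes that every dropout has a disqualifying gap. If stop days were uniform, 13 × 0.26 is about 3 patients and 13 × 0.125 about 2.
- *One arm is biased more than the other.* The documents give no discontinuation rates by arm.
- *The futility analysis is altered.* SAP 6.20 names significant noncompliance as a possible deviation and excludes some deviations before Week 12, while SAP 6.21 keeps early discontinuers in. The governing criteria are in a separate document, so any link through this formula is something to check and cannot be asserted.

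It is also fair that Protocol 7.6 and 10.3.2.4 leave the detail of compliance to the SAP, and that the Protocol 7.6 exception speaks of product withheld, which SAP 6.8 partly honours by subtracting interruptions. That latitude does not explain counting doses that nobody prescribed. Finally, adverse-event stops are not hidden: SAP Table JAHV.6.11 reports permanent discontinuation due to adverse events, and SAP 6.6 gives reasons by treatment.

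**Conclusion.** The point holds in a limited form. As written, SAP 6.8 counts the days from last dose to the discontinuation visit as missed doses, and so understates the proportion compliant. The classification changes for an otherwise adherent patient only when that gap is at least 25% of the on-drug days. That means early stops or a late discontinuation visit: DBW stops up to day 90 if the next 28-day visit is used, or up to day 28 with a 7-day gap. These figures assume full adherence until stopping and no interruptions; the share of stop days is not a share of patients.

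The consequence is small. Compliance is descriptive, the DBW population is all randomized patients, and the primary stratified log-rank test censors patients who discontinue without flare at their treatment discontinuation date. None of these uses the compliance figure. The rule is still wrong as stated and at odds with Protocol 7.6 and the SAP's own exposure definition, so it is worth correcting.

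**What to change.** In the expected-dose formula of SAP 6.8, replace the date of visit by *the earlier of the date of visit and the date of last dose before permanent discontinuation*. This also removes any dependence on which visit is taken as the discontinuation visit for patients who remain in the study off drug.

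The cost is one phrase and one line of programming. The last-dose date is already needed for the exposure calculation in SAP Table JAHV.6.10, so no new data are required. If the SAP can no longer be amended, the change and its reason can be recorded in the clinical study report, as Protocol 10.3.1 allows for changes that do not alter a principal feature of the protocol.

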6.9. Concomitant Therapy

Summaries of previous and concomitant medications will be provided by analysis population. .

At screening, previous and current JIA treatments are recorded for each patient. A summary of previous medications used for JIA, including vaccination with tetanus, diphtheria, and pertussis (TDaP) and/or pneumococcal conjugate and medications that are discontinued after screening and before the first dose of study drug, will be prepared using frequency counts and percentages by preferred medication name, with preferred medication names sorted by frequency. Concomitant therapy will be recorded at each visit and will be classified similarly. An additional summary for previous medications used for JIA will be created containing the reason of discontinuation.

Concomitant therapy for the treatment period is defined as therapy that starts before or during the treatment period and ends during the treatment period or is ongoing (has no end date or ends after the treatment period). Should there be insufficient data to make this comparison (for example, the concomitant therapy stop year is the same as the treatment start year, but the concomitant therapy stop month and day are missing), the medication will be considered as concomitant for the treatment period.

Summaries of previous medications will be provided for the following categories:

- previous JIA therapies
- previous JIA therapies including reason for discontinuation

Summaries of concomitant medications will be provided for the following categories:

- concomitant medications for JIA
- concomitant medications for non-JIA

Table JAHV.6.3. Concomitant JIA Therapies

Drug Class	As Needed	Chronic Use	Conditions for Use
MTX ^a	No	Yes	If on MTX, must be on a stable average dose of ≤ 20 mg/m ² /week for the 8 weeks preceding screening and must continue at that dose throughout the study
cDMARDs other than MTX ^a	No	Yes	If receiving cDMARDs (other than MTX), must be on a stable dose for at least 4 weeks prior to the screening and must continue at that dose throughout the study.
Oral corticosteroids	No	Yes	If receiving oral corticosteroids, daily doses of ≤ 10 mg/day or 0.2 mg/kg/day prednisone equivalent, whichever is less. Must be on stable dose for at least 2 weeks prior to screening and 6 weeks prior to baseline; the dose must be continued throughout the study.
NSAIDs ^b 
 • including cyclooxygenase-2 inhibitors, e.g., celecoxib 	No	Yes	
 • Must be on stable dose at least 1 week prior to baseline. • Changes in dose, discontinuation and/or introduction of new NSAIDs are only allowed for treatment of an AE.
Analgesics 
 • including local anaesthetics, e.g., lidocaine, and • topical anaesthetics, e.g., EMLA cream. 	No	Yes	
 • Must be on stable dose at least 1 week prior to baseline. • Changes in dose, discontinuation and/or introduction of new analgesics are only allowed for treatment of an AE.

Abbreviations: cDMARD = conventional disease-modifying antirheumatic drug; NSAID = nonsteroidal anti-inflammatory drug; MTX = methotrexate.

^a Concomitant use of >2 of any cDMARDs (including MTX) is not allowed.

^b For use as an anti-inflammatory agent.

6.10. Efficacy Analyses

6.10.1. Primary Outcome and Methodology

Time to disease flare (time is measured by week) is used as the primary outcome, which will be calculated as follows:

$$(\text{Date of Flare} - \text{Date of Randomization in the DBW} + 1)/7$$

The flare-ESR is calculated based on the flare definition and PedACR core criteria defined in Section 4.1, Table JAHV.4.1, Table JAHV.4.2, and Table JAHV.6.6, and uses ESR as acute-phase reactant. The detail of disease flare calculation is documented in separate disease flare and PedACR response calculation algorithm document. Patients completing the DBW period without flare will be censored at the date of completion (ie, the date of the last visit in the period).

Patients who discontinued treatment early in the DBW period without flare will be censored at the treatment discontinuation date.

The primary analysis of the study is to test for the hypotheses that baricitinib is superior to placebo in prolonging the time to disease flare in PedACR 30 responders from Week 12 to Week 44 using the DBW population.

A stratified logrank test will be used as the primary analysis method, in which the log-rank test will be stratified on the JIA categories:

- polyarticular and extended oligoarticular[combined]
- enthesitis-related JIA and JPsA[combined]

The p-value and median time to flare (if applicable) by treatment group will be reported. Treatment comparisons may also be analyzed using a Cox proportional hazards model adjusted for stratification variables. The hazard ratio with 95% CIs will be reported. The Kaplan-Meier product limit method will be used to estimate the survival curves for time-to flare. Time-to flare will also be summarized graphically by treatment group using Kaplan-Meier techniques.

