Patient visit and data collection can be done remotely for OLLI visits following the protocol visit windows. The PI/Sub-I is to document all teleconferences/remote visits in the patient's records. Site facing assessments will be completed on paper (preferably eCOA if the site is able) and patient facing assessments will be conducted in interview format with the PI/SubI or other qualified personnel documenting the patient's responses on paper. Sponsor will provide guidance for performing these assessments (CHQ-PF50, EQ-5D-Y). Patients *cannot* proceed in JAHV past Visit 9 due to the requirement of PedACR30 responder/nonresponder criteria being defined at this visit to determine eligibility for randomization into DBW phase. Because most PedACR components cannot be collected by remote assessment, patients will be terminated from JAHV at Visit 9 and offered enrollment into JAHX (long term extension).

3. Investigational product and ancillary supplies (including participant diaries)

In cases when a patient is unable to come to the site to receive trial supplies during a normal on-site visit, the site should work with the sponsor to determine appropriate actions to receive trial supplies. This may include a participant coming to the site to receive trial supplies only from site staff without full completion of a visit, a participant-approved designee coming to the site to receive trial supplies on a participant's behalf, or delivery to a participant's home.

The following requirements must be met:

- sponsor approves the alternative method of delivery, taking local regulatory requirements into consideration
- participant consents to alternate method of delivery
- site confirms the participant's receipt of the trial supplies
- site/sponsor confirms appropriate ethics review board notification
- alternate delivery of IP should be performed in a manner that does not compromise treatment blinding and ensures product integrity. The existing protocol requirements for product accountability remain unchanged.
- when delivering supplies to a participant's home:
 - participant consent must include provision of any personal information
 - site should ensure oversight of the shipping process to ensure accountability and product quality (i.e., storage conditions and intact packaging upon receipt)
- additional instructions should be provided to the participant on how to return any unused or completed trial supplies.

4. Local laboratory option

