In exceptional circumstances, to ensure patient safety and with the sponsor's prior written approval, local laboratory testing may be conducted in lieu of central laboratory testing. The local laboratory must be qualified in accordance with local regulations. Clinically significant laboratory findings must be recorded as an AE in the AE eCRF.

For patients unable to access investigator sites, laboratory testing will be conducted at least every 8 weeks in the OLLI and DBW periods. The first collection should be 8 weeks from the patient's last collected central laboratory samples.

Failure to have labs collected within the described ranges above may result in patient termination from the study.

When collecting local labs, sites should store records from the labs including results, address, certification (College of American Pathologists/Clinical Laboratory Improvement Amendments [CAP/CLIA]) status, and reference ranges. The PI/Sub-I should sign and date review of local labs per normal process and follow-up with the patient as needed. Local labs may be sent to the patient as this is standard process in clinical care.

Note: Any results that are obtained from local laboratories will need to be retained by the investigator for their respective patients.

The laboratory measures listed below are the **minimum** required in order to monitor patient safety and determine temporary or permanent discontinuation of IP. Additionally, investigators should include any symptom-based laboratory testing based on their interactions with the patients. As stated in the protocol, investigators are responsible for monitoring the overall health of their patients.

The investigators should request the following laboratory analyses for these select parameters:

- WBC
- ANC
- Lymphocyte count
- Hemoglobin
- Platelet count
- ALT, AST, total bilirubin, INR
- ESR
- Urine pregnancy

These laboratory results will allow the investigators to follow both the temporary and permanent discontinuation criteria as provided in the protocol (Section 8.1.1 Temporary Interruption of Investigational Product and Section 8.1.2. Permanent Discontinuation from Investigational Product)

5. Documentation

a. Changes to study conduct

Changes to study conduct will be documented as the following:

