- Sites will need to identify and document the details of how all participants, visits, methods, and activities conducted were affected by exceptional circumstances. All dispensing/shipment records of IP and relevant communications, including delegation, should be filed with site trial records.
- The site should document the participant's verbal consent for having remote visits and remote dispensing of IP and/or ancillaries prior to implementation of these activities.
- Source document(s) that are generated at an off-site location (e.g., participant's home) should be part of the investigator's source documentation and should be transferred to the site in a secure and timely manner.

b. Missing data and other protocol deviations

The study site should capture specific explanations for any missing data and other protocol deviations in source documents and eCRFs. While protocol deviations may be unavoidable in an exceptional circumstance, documentation of deviations and missing data will be important for data analysis and reporting.

Details of changes in analyses to specifically accommodate exceptional circumstances will be further described in the study SAP.

6. Informing ethical review boards (ERBs)

The sponsor and study investigators will notify ERBs as soon as possible to communicate implementation of changes in study conduct due to exceptional circumstances. To protect the safety of study participants, urgent changes may be implemented before such communications are made, but all changes will be reported as soon as possible following implementation.

Appendix 9. Protocol Amendment I4V-MC-JAHV(d) Summary - A Randomized, Double-Blind, Placebo- Controlled, Withdrawal, Safety and Efficacy Study of Oral Baricitinib in Patients from 2 Years to Less Than 18 Years Old with Juvenile Idiopathic Arthritis (JIA)

Overview

Protocol I4V-MC-JAHV—A Randomized, Double-Blind, Placebo-Controlled, Withdrawal, Safety and Efficacy Study of Oral Baricitinib in Patients from 2 Years to Less Than 18 Years Old with Juvenile Idiopathic Arthritis (JIA)—has been amended. The new protocol is indicated by amendment (d) and will be used to conduct the study in place of any preceding version of the protocol.

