6.10.2. Secondary Efficacy Analyses

Secondary efficacy and health outcomes analyses ([Table JAHV.6.4](#)) will be based on treatment periods with the respective population at each visit. The analysis method is described in [Table JAHV.6.5](#). There will be no adjustment for multiple comparisons.

Table JAHV.6.4. Description and Derivation of Primary, Secondary Efficacy Endpoints and Health Outcomes

Measure	Description	Variable	Derivation/Comment	Imputation Approach if with Missing Components
Disease flare	
Disease flare is defined as a worsening of $\geq 30\%$ in at least 3 of the 6 PedACR core criteria for JIA and an improvement of $\geq 30\%$ in no more than 1 of the criteria from the patient's condition at randomization baseline. In disease flare-ESR, ESR measure is used as acute-phase reactant in the core criteria.
 
 • If either the number of joints with active arthritis or the number of joints with limitation of motion are used in the calculation of flare for a study visit, then a minimum worsening of at least 2 active joints or 2 joints with limitation of motion must be present. • An active joint is defined as a joint with swelling or, in the absence of swelling, limitation of motion accompanied by pain on motion and/or tenderness. • If either the Physician's Global Assessment of Disease Activity or the Parent's Global Assessment of Well-Being are used in the calculation of flare for a study visit, then a minimum worsening of at least 20 mm in 0-100 mm visual analogue scale (VAS) must be present. • If ESR is used in the definition of "flare" and counts towards worsening, then the second value for ESR used in the calculation must be above the upper limit of normal for ESR (>20 mm/hour). 	Time to disease flare	
The details of disease flare calculation are documented in separate disease flare and PedACR response calculation algorithm document.
 
Calculation: Date of disease flare-ESR minus date of randomization+1
	
Component is missing if baseline or postbaseline value is missing. LOCF will be applied for post baseline missing values. If more than 3 components are missing, there will not be sufficient information; thus, the patient will be considered as a non-flare patient.

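### When a child cannot attend during the withdrawal period, weeks after the last real flare assessment can enter the primary analysis as flare-free time

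*SAP*

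**What the plan says.** Protocol Appendix 8 covers exceptional circumstances such as a pandemic. Item 2 is limited to the open-label lead-in (OLLI): "Patient visit and data collection can be done remotely for OLLI visits following the protocol visit windows". It gives the reason for stopping there: "Because most PedACR components cannot be collected by remote assessment, patients will be terminated from JAHV at Visit 9". Item 4 looks further: "For patients unable to access investigator sites, laboratory testing will be conducted at least every 8 weeks in the OLLI and DBW periods". Item 1 accepts telephone or video visits without naming a period. Item 5b defers the statistics: "Details of changes in analyses to specifically accommodate exceptional circumstances will be further described in the study SAP".

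Flare is built from the same components. SAP Table JAHV.6.4 requires worsening "in at least 3 of the 6 PedACR core criteria for JIA". For missing components it applies last observation carried forward (LOCF), and then: "If more than 3 components are missing, there will not be sufficient information; thus, the patient will be considered as a non-flare patient".

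For censoring, SAP 6.10.1 says: "Patients completing the DBW period without flare will be censored at the date of completion (ie, the date of the last visit in the period". A patient who stops treatment early without flare is censored on the day treatment stops. SAP 6.19 (COVID-19) provides a summary of the type of impact, listings, and a summary of COVID-19 adverse events. It changes nothing in the time-to-flare analysis.

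**The concern.** Appendix 8 accepts that a child who is not examined on site cannot be classified by PedACR, and ends participation at Visit 9 on that ground. The same obstacle applies to flare, yet off-site DBW patients are provided for with no matching rule. The SAP then has no concept of an evaluable flare assessment: follow-up runs to the last visit or to the end of treatment, whether or not flare could have been seen.

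Unassessed weeks therefore sit in the primary risk set as event-free. Flare proportions come out too low and median time to flare too long in both arms. The larger loss is on placebo, where more flares are expected. If absence is unequal between arms, the comparison itself is distorted, in either direction.

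**Working it through.** **Inputs.** From SAP 5.2: 64 per arm, two-sided 0.05, flare 35% (baricitinib) and 60% (placebo), dropout at most 10%, power about 80%. From Protocol 5.1.4 and Section 2: up to 32 weeks of DBW with 4-weekly visits. Not in the documents, so assumed: the share of patients off-site (10, 20 or 30%) and how long they stay away.

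**The plan's own figure.** With constant hazards, HR = ln 0.65 / ln 0.40 = 0.470. The mean flare rate is 0.475. If dropouts contribute nothing, events = 128 × 0.9 × 0.475 = 54.7 and Schoenfeld power is 79.7%. If they contribute half, events = 57.8 and power is 81.8%. The stated 80% reproduces.

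**What the rules do to an unexamined visit.** If the missing count is taken before LOCF, more than three missing components means non-flare. If it is taken after LOCF, the record repeats the last assessed visit, which was non-flare. Either way the visit is non-flare and time at risk continues.

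**One child.** Take a child last examined at Week 20 (8 weeks into DBW), never seen on site again, whose remote contact at Week 44 is accepted as the last visit. The chance of an unseen flare in the remaining 24 weeks is 1 − 0.65^(24/32) = 28% on baricitinib and 1 − 0.40^(24/32) = 50% on placebo.

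**Permanent absence, Kaplan-Meier flare at Week 44.** Let a share q leave permanently, with last on-site DBW week S equally likely to be 0, 4, …, 28. The expected estimate is F(32) − q × [F(32) − mean F(S)].
- Placebo: mean 0.40^(S/32) = (1 − 0.40) / [8 × (1 − 0.40^(1/8))] = 0.693, so mean F(S) = 0.307. The estimate is 0.60 − 0.293q.
- Baricitinib: mean 0.65^(S/32) = (1 − 0.65) / [8 × (1 − 0.65^(1/8))] = 0.835, so mean F(S) = 0.165. The estimate is 0.35 − 0.185q.

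Simulation (exponential flares, 4-weekly detection, 10% dropout, unstratified log-rank, 3,000 or more trials per scenario, Monte Carlo error up to about 0.8 points) agrees with these values to within about a point and adds power:

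| Permanently off-site, both arms | KM flare, SAP rule (bari/placebo) | Power, SAP rule | Power, last-evaluable censoring |
|---|---|---|---|
| 10% | 33/57% | 78% | 79–80% |
| 20% | 31/54% | 74–75% | 75–77% |
| 30% | 29/51% | 70–71% | 73–74% |

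Under last-evaluable censoring the Kaplan-Meier estimates stay at about 35/60% throughout. The difference in flare proportions under the SAP rule is 25 − 10.8q points, about 22 at q = 0.30.

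**Temporary absence.** With spells of 8 or 12 weeks at the same shares, the SAP rule gives 34.0–34.8% and 59.0–59.8%. Power is 80–81%, against 79–82% with last-evaluable censoring. Over 8 to 16 weeks the bias is about 0 to 2 points and power does not change materially.

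**Permanent absence that differs by arm.**
- 10% baricitinib, 20% placebo: KM 33/54%. Power is 67–69% under the SAP rule and 78% with last-evaluable censoring.
- No true effect (60% flare in both arms), 30% baricitinib, 10% placebo: the placebo formula gives 51% and 57%, a spurious 6-point difference. The two-sided false-positive rate is 9.2–9.6% under the SAP rule and 5.1–5.4% with last-evaluable censoring.
- No true effect (47.5% flare in both arms), 20% and 10%: 6.4% against 5.1%.

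**The case against.** Several counter-arguments stand in part.

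- **Retention is implied, not stated.** A reader might infer that Appendix 8 keeps off-site children in the DBW period. It never says so. Item 2 confines remote data collection to the OLLI, changes need case-by-case sponsor approval, and item 4 says missed laboratory tests may end participation. The inference is still reasonable. Item 4 names the DBW period, item 3 asks that alternative drug delivery protect the blind (only the DBW is blinded), and no removal rule appears.
- **Non-flare is not automatic.** Local ESR is on the minimum laboratory list, and CHAQ function and the parent's global are completed by the parent. If all three are obtained, exactly three components are missing, which is not more than three, and flare remains possible. But if the carried-forward components show no worsening, all three fresh ones must worsen, and ESR is required only 8-weekly.
- **Absence may be short.** Appendix 8 calls its provisions temporary. A child who returns can have a flare detected late, and a flaring child may be seen at an unscheduled visit. This is the main reason to expect a small effect.
- **Unseen detail.** The SAP puts flare and missing-data details in a separate algorithm document that is not public and might define evaluability. The SAP also does not say whether a telephone contact counts as the last visit. The censoring rule, however, is in SAP 6.10.1 itself.
- **Most of the power loss is lost information.** That is correct: with equal shares, better censoring recovers only 1 to 3 points.

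**Conclusion.** The point holds as a defect in the censoring rule. As written, the SAP can count time as flare-free when flare could not be assessed, and the protocol's promise of adapted analyses is not met for the primary endpoint. The sample size is not in error.

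The size depends on an off-site share and duration that the documents do not give. With equal permanent absence of 10 to 30%, both flare estimates are low by about 2 to 9 points and the treatment difference shrinks slightly. With temporary absence the effect is close to nil. The serious case is permanent absence that differs by arm, where either power or the type I error rate suffers. Nothing in the documents shows that this occurred.

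A reader might go further and conclude that the primary result is invalid, or that a placebo flare estimate near 51% is to be expected. The documents do not support that: it needs 30% of children never to return and no flare to be detected among them.

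**What to change.** In SAP 6.10.1, censor patients without flare at the last DBW visit at which flare status could be determined from components actually assessed at that visit, not carried forward. This should cover completers and early discontinuers alike, and missed as well as remote visits. Use one evaluability criterion both for declaring flare and for counting flare-free time. If a partly assessed visit could count as a flare but not as flare-free time, flare rates would be pushed up. Align the separate algorithm document and state whether a remote contact is a visit for this purpose.

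Keep the current rule as a sensitivity analysis, and report the number of non-evaluable DBW visits by arm. Appendix 8 items 1, 2 and 4 must be reconciled on patients who cannot attend in the DBW period; which rule should apply is for the sponsor to decide.

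The cost is one SAP sentence, one extra run and one table, with no new data. The drawbacks are slightly less nominal follow-up and reliance on the assumption that going off-site is unrelated to flare risk.
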